The objective of this study is to measure whether activation of a cellphone blocking device results in a decrease in the frequency of drives in which the phone is unlocked and the total proportion of time in which a cellphone is being used at non-zero speeds by teen drivers and to determine the incidence of handheld cellphone use while driving and its relationship to incoming text messages and driving conditions in a teen driver cohort.

Study Design:

Research participants will be recruited to take part in a randomized control trial. Participants' cellphone use will be observed during an initial baseline period. Participants will then be randomly assigned to one of four conditions (education only (control), opt-in blocking, opt-out blocking, and opt-out blocking with parental notification).

[figure not shown]
Setting/Participants:

High school students who are age 16 or 17 at the start of the study that drive an average of 4 trips per week and hold a valid driver's licenses will be recruited. Other inclusion criteria include living with a parent/guardian, having their own smartphone (iPhone 4S or newer or Android 4.3 or newer) with data plan, primarily driving one car, admitting to texting while driving at least once in the past month, do not currently use a cellphone blocking app or device, and that a parent will be willing to install the device and adjust the settings as necessary.

Study Interventions and Measures:

A cellphone blocking device (DriveID) will be mailed or given directly to participants. DriveID will measure all teen participant cellphone use while the cellphone is in the car for the first four weeks. During the intervention period (Weeks 5-8), participants will be placed into one of the four conditions (one control, three blocking) that they have been randomized to. At the beginning of Week 5, the participant's DriveID will either be flipped into a cellphone blocking mode where the phone will lock when being used while driving or remain in a control mode. A two week follow-up phase will occur after the intervention, during which participants may choose which group they would like to try. Surveys and an interview will also be administered as part of this study.

FIGURE 1: STUDY DIAGRAM

Measurements:

Cellphone use while driving	—————→		
Participant Survey	X	X	X*
Educational Information		X	
Interview			X

* Participant chooses mode for follow-up phase

1 BACKGROUND INFORMATION AND RATIONALE

1.1 Introduction

In the U.S. in 2012, 3,328 people were killed in crashes involving a distracted driver, and an additional 421,000 people were injured (up from 387,000 in 2011).¹ Drivers under the age of 20 represent the largest proportion of drivers who were distracted. Motor vehicle crashes are the leading cause of death in teens in the U.S.,² and for drivers aged 15-19 involved in fatal crashes, 21% of distracted drivers were distracted by the use of cellphones.¹ In a recent New England Journal of Medicine study, the risk of crashes in teen drivers was 3 to 8 fold higher if the driver was dialing or texting their cellphone,³ an effect similar to having a blood alcohol concentration of 0.1 (above the legal limit of 0.08).⁴ Nearly half of U.S. high school students admit to texting while driving in the last 30 days, despite the majority knowing that texting while driving is harmful.

Legal bans, public awareness campaigns, pledges, and a myriad of smartphone apps to reduce cellphone use while driving have had little effect on curbing the epidemic.⁵ One reason these efforts have had limited success is that texting has been shown to be a compulsion in teens driven by present biased-preferences. Nearly 90% of teens expect a response to a text within 5 minutes, and the compulsion to respond is stronger for messages from close social contacts, such as a significant other.⁶ This suggests that behavioral-economic interventions such as immediate and frequent incentives are needed to offset the disutility caused by not being able to communicate by cellphone while driving.⁷ If proven to be effective, incentives could be scaled up via auto insurance discount contributions, school programs, and parental contributions.

1.2 Name and Description of Intervention

DriveID was released in December of 2013 as a device to overcome a technological barrier in being able to accurately measure whether a driver's cellphone is being used while driving. It is a solar-powered Bluetooth signaling technology placed on the car windshield. DriveID can measure type of cellphone use while driving and be configured to block a driver's cellphone use while the vehicle is in motion. There is no physical interaction with the DriveID device other than installation.

The device is placed on the windshield and an app is downloaded on to the phone. Online configuration of the device settings takes approximately 3-5 minutes. After the initial installation, the device is always on and interacts with the user's cellphone in the background. Only the cellphone with the corresponding DriveID application is monitored by the DriveID device. The DriveID device directly accesses the vehicle's driving metrics and can be set to lock the phone at speeds as low as 1 mph. Device setup is flexible to allow for specific smartphone applications like navigation and maps. The blocking function cannot be deactivated without permission of the account holder.

The study intervention involves randomization into one of four conditions: 1 control condition and 3 blocking conditions (opt-in blocking, opt-out blocking, and opt-out blocking with parental notification). For the control condition, the device will collect information about cell phone use, but no blocking functions will be activated. For opt-in blocking, the

participants will have to initiate the app when entering the vehicle; the blocking settings will be pre-set to block incoming calls and text messages only. For opt-out blocking, the device will automatically turn on when the teen begins driving and will be set to the same pre-set blocking configuration as opt-in blocking. For opt-out blocking with parental notification, the device will automatically turn on when the teen begins driving. The blocking settings will be pre-set to block all incoming calls and text messages. If teens override the blocking feature, a parent/guardian will receive an instant notification in the form of an email. Parents/guardians will also have the ability to increase the settings to block outgoing calls and all other cellphone functions (i.e. applications). Furthermore, if teens in any condition tamper with the DriveID device, delete the corresponding application from their smartphone, or disable Bluetooth capabilities, an email will be sent to the parent/guardian and a member of the study team.

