4.3.2 Intervention

At the completion of the baseline phase, all participants will receive an email to an educational website where they can learn about the dangers of distracted driving (<http://endddd.org>). Teens will also complete a survey.

Cellcontrol will remotely flip the participant's DriveID into a cellphone blocking mode for those in the three blocking conditions of the study on the first day of the intervention period. Teens randomized into the control group will continue with DriveID as is (information regarding cell phone use will continue to be collected, but no blocking will occur). In the blocking conditions, the phone will lock when being used while driving, but the locking function can be overridden.

Coded data on primary and secondary endpoints will be automatically uploaded daily whenever the phone has a Wi-Fi or cellular data connection to the Cellcontrol server and then exported through an encrypted, secure internet connection to Penn's Way to Health IT Platform for management and analysis via linkage of a study ID.

All parents will have the option to check teen's phone use while the vehicle is in motion on the website (<https://account.cellcontrol.com/login.php>) during weeks five to ten. Parents in the opt-out blocking with parental notification group will receive a notification every time the phone is being used while the vehicle is in motion.

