5.7 Safety Evaluation

This is a minimal risk, behavioral intervention study. Physical risk is no more than the risks already caused by distracted driving from handheld cellphone use. The intervention directly lowers the risk of distracted driving by blocking incoming phone calls and texts and locking the phone while the participant is driving. The participant may unlock the phone in any of the conditions with the swipe of a finger where they will then be brought to their typically screen. If participants have their phone password protected, they will still need to enter their password in order to use the phone. The extra swipe to dismiss the cellphone blocking technology is no more dangerous than unlocking the phone normally.

Participants will have no interaction with the physical DriveID device after installation. There are no expected serious adverse events related to the intervention or participation in this study.

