7.1.4 Opt-out Blocking with parental notification Group

The blocking setting for the opt-out blocking with parental notification group participants will turn on by default while driving. The restrictions will be pre-set to block all incoming calls and text messages while the vehicle is in motion. Parents/guardians will receive a notification every time the teen overrides the block at non-zero speeds. Parents/guardians will have the option to also block outgoing calls as well as all other cellphone functions (i.e. applications). Number of unlocks can also be monitored through logging in to the DriveID website.

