9.4.2 Risk Assessment

Despite care taken in the study design to minimize risk exposure to participants, it is acknowledged that there is minimal risk to participants.

Loss of confidentiality is a potential risk of participating in this study; however, the safeguards put in place by *Way To Health* and the Mixed Methods Research Lab (Section

9.2) will reduce this likelihood. The members of the study teams will follow necessary precautions to ensure that all collected data is not shared with unauthorized individuals or groups.

As part of this study, teens will be driving with a cell phone blocking device present and operating in the vehicle. These teens are eligible for the study because they admit to texting while driving. This study will not require them to interact with their phones while driving any more than they would normally choose to on their own. We will encourage teens throughout the study to drive safely and not to use their cell phones while driving.

It is possible that participants may feel uncomfortable answering some of the interview questions. They will be made aware before the start of the interview that this is a risk associated with participation in the interview and will be reminded that they do not have to answer any questions which make them uncomfortable.

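### Parents in the notification arm are emailed while the teen is probably still driving, and the visible protocol neither tells them to hold off calling or texting nor considers this route as a risk

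*Combined protocol and SAP*

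**What the plan says.** Three sections describe the notice. Section 1.2: on an override, "a parent/guardian will receive an instant notification in the form of an email". Section 7.1.4: "Parents/guardians will receive a notification every time the teen overrides the block at non-zero speeds". Section 4.3.2 is wider: parents in this arm "will receive a notification every time the phone is being used while the vehicle is in motion".

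On the block itself, section 7.1.4 says: "The restrictions will be pre-set to block all incoming calls and text messages while the vehicle is in motion". On overriding it, section 5.7 says: "The participant may unlock the phone in any of the conditions with the swipe of a finger", after which the teen is back at the usual screen.

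On what parents may do, sections 1.2 and 7.1.4 let those in this arm tighten the settings to cover outgoing calls and other functions. Section 4.3.2 lets all parents look at phone use on a website in weeks 5 to 10.

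On safety messages, section 9.4.2 says: "We will encourage teens throughout the study to drive safely and not to use their cell phones while driving". Section 3.1.3 likewise addresses participants.

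**The concern.** The notice is timed to the moment when contact with the teen is least wanted. A parent who learns that the teen has just overridden the block may call or text at once, and the teen is probably still at the wheel. Section 5.7 argues that the intervention lowers risk because it blocks incoming calls and texts. A notice that invites an incoming call or text works against that argument.

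The participants are 16- or 17-year-olds who admit to texting while driving (section 3.4.1). Section 1.3 cites odds ratios for a crash or near-crash among novice drivers of 7.05 for reaching for a phone and 3.87 for sending or receiving texts. The stake is participant safety, through a route that the study's own notice could open and that the risk sections do not mention.

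**Working it through.** No figure in the plan bears on this point, so the check is a comparison of sections.

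1. **Is the teen driving when the notice goes out?**
   - Section 1.2: trigger is an override; the email is instant; speed is not stated.
   - Section 7.1.4: trigger is an override at non-zero speed.
   - Section 4.3.2: trigger is any phone use with the vehicle in motion.
   - Sections 7.1.4 and 4.3.2 both require a moving car, and section 1.2 makes the email immediate. Unless the trip is about to end, a parent who reads it promptly reads it mid-drive.

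2. **Do the statements about real-time data remove this?** Section 4.3.1 says the study team will not access data in real time. Section 9.2.2 says data will not be tracked in real time. The first is limited to the study team, and neither withdraws the parent email.

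3. **Would the block stop a parent's call or text?** This depends on a fact that is not given.
   - If incoming blocking stays on or resumes after an override, the contact is stopped.
   - If one override lifts it for the rest of the trip, the contact gets through.
   - Under the wider trigger in section 4.3.2, if the phone can be used without an override, a notice could also go out while the block is still on. The trigger and the block status therefore need to be settled together.

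4. **What are parents told?** The only parental actions described are tightening the settings and viewing use online. The set-up meeting in section 4.1 covers questions and understanding of risks and benefits; no content about notices is listed. The safe-driving messages in sections 3.1.3 and 9.4.2 go to participants and teens.

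5. **Do the risk sections cover it?** Section 5.7 discusses the extra swipe and the device. Section 9.4.2 says the study will not require more phone interaction than teens would choose. That concerns interaction the study requires, not contact it might prompt. Neither section mentions the notice.

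6. **How would prompted use enter the results?** The contrast in section 6.3.2 is each arm against control by intention to treat. Notification is a defining part of this arm, so what parents do on receiving it is part of the effect being estimated. A call received or a text read could count in a secondary endpoint (section 6.2). It need not add to the primary endpoint, unlocks per hour (section 6.1), because section 5.3 tabulates talk time, other usage and unlocks separately. Section 5.3 lists no caller or sender identity, so prompted use could not be picked out afterwards.

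**The case against.** The strongest reply is that the mechanism is a chain of unproven steps: the parent must see an email mid-trip, decide to contact the teen, get past a block on incoming calls and texts, and be answered. The documents support none of these with data, and the only responses they describe are tightening the settings and viewing use online. This stands as a limit on how strongly the point can be put. It does not close the gap, because the block status after an override is left open and the notice is sent in motion by design.

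Three stronger statements that a reader might infer are not supported:

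- **That parents are definitely not told to wait.** The consent pages were removed, and the text of the email and the content of the meeting are not in the documents. What can be said is that the visible intervention, procedure and risk sections are silent.
- **That the protocol's rationale shows teens will answer a parent.** Section 1.1 says "the compulsion to respond is stronger for messages from close social contacts", but its example is a significant other. The statement that nearly 90% of teens expect a response within 5 minutes describes their expectations about texts, not how they react to a parent.
- **That parental prompting can occur in this arm only.** All parents may view phone use online in weeks 5 to 10, and tamper emails go to parents in any condition (section 1.2). Only the instant override notice is specific to this configuration.

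**Conclusion.** The point holds as a small participant-safety gap. The notice is sent while the teen is probably still driving, the visible sections give parents no guidance on contacting the teen, and sections 5.7 and 9.4.2 do not consider the route. The risk is foreseeable and unquantified. The verdict assumes that no such instruction appears in the material not available here and that incoming contact can get through after an override. If the block returns at once, the hazard largely disappears, and the protocol should say so.

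A reader might go further and infer that the arm-versus-control result is biased toward no benefit, and try to put a number on it. The documents do not support this. Prompted use may mask some of the deterrence that notification is meant to produce, but under intention to treat it is part of what this arm does. Any figure would need an override rate, the share of notices leading to contact, the share of contacts picked up and a true effect. The documents give none of these, the prompted share could be zero, and deterrence could outweigh it.

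Separately, the trigger in sections 1.2 and 7.1.4 (an override) and in section 4.3.2 (any phone use in motion) is inconsistent, and the sections must be reconciled.

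**What to change.** - At the set-up meeting in section 4.1, in section 7.1.4, and in the notification email if its text can be edited, tell parents that the teen is probably still driving and not to call or text until the trip is over. The meeting takes place before assignment (section 9.1.1), so the message would go to all parents. That also covers families who choose the notification configuration in the follow-up period (section 3.1.4).
- Add this route to the risk assessment in section 9.4.2.
- State whether incoming blocking resumes after an override.
- Reconcile the notification trigger in sections 1.2 and 7.1.4 with section 4.3.2.

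The cost is one line in the meeting script and, where possible, in an automated email, plus short protocol edits. The analysis is unaffected. The downside is that the notice becomes slightly more prescriptive to parents, which marginally changes the intervention being tested.

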1.3 Findings from Non-Clinical and Clinical Studies

The largest, most rigorous study of the crash risk associated with distraction from cellphone use was published in the *New England Journal of Medicine* in January 2014. The authors conducted two studies on the relationship between the performance of secondary tasks, including cell-phone use, and the risk of crashes and near-crashes. To facilitate objective assessment, accelerometers, cameras, global positioning systems, and other sensors were installed in the vehicles of 42 newly licensed drivers (16.3 to 17.0 years of age) and 109 adults with more driving experience.

During the study periods, 167 crashes and near-crashes among novice drivers and 518 crashes and near-crashes among experienced drivers were identified. The risk of a crash or near-crash among novice drivers increased significantly if they were dialing a cell phone (odds ratio, 8.32; 95% confidence interval [CI], 2.83 to 24.42), reaching for a cell phone (odds ratio, 7.05; 95% CI, 2.64 to 18.83), sending or receiving text messages (odds ratio, 3.87; 95% CI, 1.62 to 9.25), reaching for an object other than a cell phone (odds ratio, 8.00; 95% CI, 3.67 to 17.50), looking at a roadside object (odds ratio, 3.90; 95% CI, 1.72 to 8.81), or eating (odds ratio, 2.99; 95% CI, 1.30 to 6.91). Among experienced drivers, dialing a cell phone was associated with a significantly increased risk of a crash or near-crash (odds ratio, 2.49; 95% CI, 1.38 to 4.54); the risk associated with texting or accessing the Internet was not assessed in this population. The prevalence of high-risk attention to secondary tasks increased over time among novice drivers but not among experienced drivers.

The authors concluded that the risk of a crash or near-crash among novice drivers increased with the performance of many secondary tasks, including texting and dialing cell phones. The study was funded by the Eunice Kennedy Shriver National Institute of Child Health and Human Development and the National Highway Traffic Safety Administration.

There is one previous field study using Cellcontrol's cellphone blocking/filtering technology to reduce cellphone use while driving, which was funded by the National Highway and Traffic Safety Administration (NHTSA Contract DOT HS 811 863) and carried out by investigators at the University of Michigan. The abstract of the full report published online in December 2013 states:

Forty-four participants each received a cell phone filtering/blocking application on their employer-provided cell phones for 9 weeks. During the first and last 3 weeks, cell phone activity including calling, text messaging and application use was simply recorded in the background. During the middle 3 weeks, the cell phone filtering/blocking software was active, meaning that anytime the application sensed that the phone was moving faster than the pre-set speed threshold, all phone activity was blocked. Objective data on participants' phone use behavior and subjective data (from a questionnaire) on participants' acceptance were collected. Additionally, the impact on an organization attempting to implement a similar program employing cell phone filtering/blocking was examined. During the blocking period, participants initiated a higher proportion of their calls when stopped than when the blocking software was inactive. Also, during the blocking period, participants answered a much smaller proportion of incoming calls while driving, and outgoing calls were placed at a lower mean speed. Participants were neutral in their opinions on whether they received a safety benefit from the cell phone blocking.

1.4 Compliance Statement

This study will be conducted in full accordance of all applicable Children's Hospital of Philadelphia Research Policies and Procedures and all applicable Federal and state laws and regulations including 45 CFR 46. All episodes of noncompliance will be documented.

The investigators will perform the study in accordance with this protocol and will report unanticipated problems involving risks to subjects or others in accordance with The Children's Hospital of Philadelphia IRB Policies and Procedures and all federal requirements. Collection, recording, and reporting of data will be accurate and will ensure the privacy, health, and welfare of research subjects during and after the study.

